11.8 Resources necessary for human subjects protections

1. Abstract

Increased physical activity by walking further or more vigorously may prevent or delay the development of Alzheimer's Disease and Related Dementias (ADRD) but reaching higher levels of activity and maintaining it as a long-term habit is difficult to do. This project will use concepts from behavioral science to create a game older adults can play in order to increase their levels of activity while having fun doing it. The game is played with a support partner who is a spouse, family member, or close friend who provides feedback and encouragement to help the game-player reach activity goals and maintain them as habits over time. Participants in the game will use their own smartphone and a wristwatch that tracks activity (such as a FitBit, provided by this study) to set goals, get feedback, and play the game for 12 weeks. Participants will be asked to continue wearing the wristwatch for another 6 weeks to track activity after the game is over. To determine the effectiveness of this game, we will randomly assign 50 people to the game and 50 people to only get the wristwatch but no game component. All participants in this study will be recruited from an online registry of adults age 55-75 who have not been diagnosed with Alzheimer's (GeneMatch) which offers genetic testing on risk for ADRD to all participants. We

will recruit participants to our study who have elevated genetic risk as well as those without specific genetic risks to see if either group responds differently to the game.

2. Overall objectives

The primary objective is to assess the effectiveness of a social incentive-based gamification intervention to increase physical activity over 12 weeks with follow up of 6 weeks after the intervention concludes. We will explore whether participants who know they are higher risk (carriers of the APOE4 gene) are more responsive to the intervention than those who know they are at average risk (non-carriers of APOE4). We will also explore the feasibility of collecting measures of cognition and function remotely using standardized instruments by telephone or video calls.

3. Aims

3.1 Primary outcome: change in mean daily step count from the baseline period to the end of the 12-week intervention period.

3.2 Secondary outcome: mean daily step count during the 6-week follow up period after the end of the intervention.

3.3 Exploratory outcomes: functional measures will include the Timed Up and Go and 30-second Chair Stand Test.^{45,46} Cognitive measures will include Verbal Naming, Category Fluency, Trail Making, Number Span, and Blind MOCA.⁴⁷

4. Background

Systematic reviews have demonstrated that higher levels of physical activity are associated with lower risk of developing ADRD even with modest increases in low-intensity exercises.¹⁻³ Physical Activity Guidelines from the U.S. Department of Health and Human Services also recommend ≥ 150 minutes/week of moderate intensity physical activity (e.g., brisk walking) for older adults to reduce risks of functional and cognitive decline (including ADRD specifically).^{4,5} Physical activity is also recommended by the NIA for people with ADRD and taking daily walks with a support partner is specifically encouraged.⁶ Some studies have suggested higher intensity exercise or multi-component interventions may have the greatest impact but the sustainability and scalability of these approaches are major limitations.

Interventions leveraging behavioral economics (BE) to increase physical activity have demonstrated sustainability over prolonged periods after the end of the intervention;⁷ however, these approaches have not been applied to populations at risk for ADRD specifically. There are several key components of these interventions which warrant testing in this population. First, gamification leverages BE concepts to motivate behavior change. Gamification is the use of game-design elements such as points and levels in non-game contexts.^{9,10} Gamification is an

appealing approach to increase engagement in healthy behaviors because it makes the “hard stuff” fun by turning obligations into goals and challenges.¹⁰ Second, mobile technologies which are increasingly used by older adults¹¹ can be used to accurately,¹² and unobtrusively help set and maintain specific daily and weekly activity goals. Third, social incentives can be used to enhance these effects and reinforce habit formation to prevent regression. Social incentives are powerful influences that motivate individuals to change their behaviors based on social ties or connections.¹⁴⁻¹⁷ For example, an individual’s mobility is higher when a family member or friend has increased mobility.¹⁷ On closer inspection, such interactions contain many powerful levers to change human behavior including peer support, accountability, and collaboration. Since social networks are ubiquitous, approaches that harness social incentives could be scaled more broadly at lower cost than interventions relying on health care professionals to motivate and monitor physical activity in older adults at risk for ADRD. Our group has successfully used gamification, mobile technologies, and social incentives to increase activity in several non-ADRD populations.

One challenge to studying behavioral interventions to improve physical activity in the ADRD population has been enrollment with most studies to date enrolling from clinics which limits sampling; prior studies have also used variable definitions of “elevated risk” for dementia. In this study, we identify and recruit participants utilizing a novel, national cohort of individuals with quantifiable risk using genetic testing from the GeneMatch study.^{18,19}

5. Study design

5.1 Design

We will conduct a 2-arm, randomized, controlled trial over 12 weeks with 6 weeks of follow-up (18 weeks total) that compares a control group that uses a wearable device to track physical activity to an intervention group that uses the same wearable devices and receives a supportive social incentive-based gamification intervention to adhere to a step goal program. In phase 1 (2 weeks), participant step counts will be monitored and baseline step count will be estimated. In phase 2 (12 weeks), participants will be randomly assigned to the control or intervention group and will set step count goals. In phase 3 (6 weeks), interventions will cease and participant step counts will be monitored. Participants will be considered enrolled in the trial if they complete the run-in period and then are randomized.

5.2 Study duration

The study will begin in Summer 2021. The primary intervention period is 12 weeks. Participants will be enrolled for approximately 20 weeks (2 week run-in, 12 week intervention, 6 week follow up). We expect the entire study to take approximately one year to conduct and analyze outcomes.

5.3 Target population

Adults age 55-75, own a smartphone, enrolled in GeneMatch, know their genetic testing results (APOE4), and able to provide informed consent

5.4 Accrual

We will aim to enroll and randomize 100 participants. We estimate a standard deviation of 2500 steps and a sample of 100 participants allocated in a 1:1 distribution (50 in each arm), will ensure at least 80% power to detect a 1000 step difference. This calculation assumes a 10% dropout rate and a conservative Bonferroni adjustment of the type I error rate with a 2-sided alpha of 0.017.

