Similar to our prior work,^{22,44,54} the primary analysis will fit mixed effect regression models to evaluate changes in physical activity (steps per day and minutes of MVPA) adjusting for each participant's baseline measure, time using calendar month fixed effects, participant random effects, and accounting for repeated measures. Secondary analyses will fit a fully adjusted model including other variables of interest such as participant demographic characteristics and comorbidities. We will also conduct a-priori exploratory subgroup analyses for participants with elevated risk (APOE4 carriers) and higher levels of social support on 1o and 2o outcomes. For these outcomes, we estimate a standard deviation of 2500 steps and a sample of 100 participants allocated in a 1:1 distribution (50 in each arm), will ensure at least 80% power to detect a 1000 step difference. This calculation assumes a 10% dropout rate and a conservative Bonferroni adjustment of the type I error rate with a 2-sided alpha of 0.017.

In exploratory analyses, we will compare results from virtual functional and cognitive tests at the beginning of the study (after randomization) with results during the follow up period (after intervention ends). We do not anticipate major changes in these measures and are not powered to detect minor changes – these are feasibility measures to demonstrate we can conduct virtual performance tests at multiple intervals only.

We will also conduct exploratory subgroup analyses of factors that may influence our primary outcome (change in mean steps/day) such as participant-reported social support and neighborhood walkability as determined by address/zipcode. These are factors that have been associated with steps in our prior work but this pilot will not adequately powered to detect statistical significance (we will explore for trends only).

10. Investigators

[name], MHS, MA is the Principal Investigator (PI). He is the Director of Penn Center for Evidence-based Practice; his research focuses on outcomes of hospitalization for older, vulnerable adults during transitions of care and mobile technologies to engage this population.

[name] is Co-Director of the Penn Memory Center and Director of the Penn Program on Precision Medicine for the Brain (P3MB). His research focuses on quality of life and ethical issues of disclosure of gene and biomarkers of Alzheimer's disease risk in older adults.

11. Human research protection

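### The power statement is wrong on its own inputs: about 30% power for a 1000-step difference, not at least 80%

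*Combined protocol and SAP*

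**What the plan says.** Section 5.4 (Accrual) sets out the whole calculation:

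- Variability: "We estimate a standard deviation of 2500 steps".
- Size and allocation: "a sample of 100 participants allocated in a 1:1 distribution (50 in each arm").
- Claim: the sample "will ensure at least 80% power to detect a 1000 step difference".
- Attrition and error rate: "This calculation assumes a 10% dropout rate and a conservative Bonferroni adjustment of the type I error rate with a 2-sided alpha of 0.017".

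Section 9 (Analysis plan) repeats the same figures. Section 3.1 defines the primary outcome as "change in mean daily step count from the baseline period to the end of the 12-week intervention period".

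Section 9 plans a mixed-effects model adjusted for the baseline measure and calendar month, with participant random effects. Neither section says what the SD of 2500 describes: change, a participant's mean level, or single-day counts. Neither gives a correlation between baseline and follow-up, an intraclass correlation or a residual SD.

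**The concern.** The standardised difference is 1000/2500 = 0.4. Fifty per arm is well short of what a difference of that size needs for 80% power, even at alpha 0.05, and the plan uses a stricter alpha and allows for dropout.

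Section 2 makes effectiveness the primary objective. Section 9 disclaims power for the functional and cognitive measures and for the social-support and walkability subgroups, but not for the primary comparison, which therefore looks adequately powered by contrast. A reader who trusts the 80% could take a non-significant result as evidence against a 1000-step effect when the trial had little chance of detecting one. The plan does not say how a non-significant result will be read, so this is a judgement about consequence rather than something the documents state.

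**Working it through.** **Inputs (sections 5.4 and 9).** Difference d = 1000; SD s = 2500; 50 randomised per arm; 10% dropout, so n = 50 × 0.9 = 45 evaluable per arm; two-sided alpha 0.017.

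**Attempt to reproduce the stated 80%.** Standard error of the difference = s√(2/n) = 2500 × √(2/45) = 527. Expected z = 1000/527 = 1.897. Critical value for two-sided 0.017 = 2.387.

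Power (normal approximation) = Φ(1.897 − 2.387) = Φ(−0.489) = 31.2%. The noncentral t gives 30.2%. The stated figure is not reproduced.

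**Relaxing the stated inputs one at a time:**

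| Evaluable per arm | Two-sided alpha | Power (normal) | Power (t) |
|---|---|---|---|
| 45 | 0.017 | 31.2% | 30.2% |
| 50 (no dropout) | 0.017 | 34.9% | 33.9% |
| 45 | 0.05 | 47.5% | 46.7% |
| 50 (no dropout) | 0.05 | 51.6% | 50.8% |
| 100 (total read as per arm) | 0.017 | 67.1% | 66.3% |
| 100 (total read as per arm) | 0.05 | 80.7% | 80.4% |

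Among these, about 80% appears only with 100 per arm, no dropout and alpha 0.05. A one-sample formula with n = 50, no dropout and alpha 0.05 also gives 80.7%. Both contradict the stated design and alpha. I do not claim that either explains the error.

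**What 80% would require at alpha 0.017:**

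- Sample size: n = 2s²(z₁ + z₂)²/d² = 2 × 2500² × (2.387 + 0.842)²/1000² = 130.3, so 131 per arm (132 by t). Dividing by 0.9 gives 146 to 147 randomised per arm, roughly three times the planned 50.
- Detectable difference with 45 per arm: 527 × (2.387 + 0.842) ≈ 1,701 steps (normal) or 1,730 (t). At alpha 0.05 it is 1,477 or 1,493.
- SD giving 80% power for 1000 steps with 45 per arm: 1,469 (normal) or 1,445 (t).

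**Baseline adjustment (45 per arm, alpha 0.017, t-based; the correlations r are assumptions).**

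- *If 2500 is the SD of change*, with equal variances at the two times, the residual SD is 2500√((1 + r)/2). Power is 60% at r = 0, 47% at 0.3, 41% at 0.5, 36% at 0.7 and 34% at 0.8. It falls as r rises, and none of these values reaches 80%.
- *If 2500 is the SD of the step level*, the residual SD is 2500√(1 − r²). Power is 41% at r = 0.5, 59% at 0.7, 78.7% at 0.81 and 80.9% at 0.82.

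**Single-day reading (the intraclass correlations are assumptions).** If 2500 is the SD of one day's count and each participant's mean covers 84 days, the SD of that mean is 2500√(ICC + (1 − ICC)/84). Without baseline adjustment, power is 80.8% at an ICC of 0.32, 79.5% at 0.33 and 78.2% at 0.34.

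**Precision.** With 45 per arm and SD 2500, the 95% confidence interval half-width is about 1.99 × 527 ≈ 1,050 steps, so an estimate of zero would not exclude a 1000-step effect.

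**The case against.** The best reply is that 30% is conditional. Section 5.4 does not define its SD, and the section 9 model is not a plain two-sample comparison. It adjusts for baseline and uses repeated daily measures, both of which can reduce the error variance.

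Two readings can reach 80%. One is an SD of level with a baseline correlation of about 0.82. The other is a single-day SD with an intraclass correlation of about one third or less. If the single-day reading is combined with adjustment for a seven-day baseline, and all days within a person are assumed equally correlated, the residual SD is about 520 to 720 steps at intraclass correlations of 0.3 to 0.7, and power exceeds 80%. That structure is optimistic, because it allows no drift in a person's activity over the study.

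This much stands: the documents do not establish that the planned analysis has exactly 30% power. It does not rescue the sentence, because every route to 80% needs a quantity the plan does not give. The stated primary outcome is a change, and if 2500 is the SD of that change, none of the correlations tried (0 to 0.8) brings the adjusted power to 80%.

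Section 9 also calls the study a pilot, but that remark concerns the exploratory subgroup factors, not the primary outcome.

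**Conclusion.** The concern holds. On the plan's own figures, power for a 1000-step difference is about 30% (31% by normal approximation), some 50 percentage points below the claim. The chance of missing a true effect of that size is about 70%, and the difference detectable with 80% power is about 1,730 steps.

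These figures rest on 2500 being the SD of the analysed participant-level quantity, on 45 evaluable per arm and on the stated alpha. A higher power is possible under a different definition of the SD or with a strong baseline correlation, but the documents supply neither, so the assurance of at least 80% is unsupported as written. It is a central design claim and should be corrected.

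**What to change.** Replace the power sentence in both section 5.4 and section 9. Suggested text:

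> With 45 evaluable participants per arm, an SD of 2500 steps and two-sided alpha 0.017, power for a 1000-step difference is about 30%; the difference detectable with 80% power is about 1,730 steps.

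If alpha 0.05 is what the sponsor intends for the primary comparison, the corresponding figures are 47% and about 1,490 steps. The present 0.017 is close to 0.05/3, and the two-arm plan does not say which three comparisons it covers.

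If the sponsor had a baseline-adjusted or repeated-measures calculation in mind, the text should say what the 2500 measures and give the assumed correlation, intraclass correlation or residual SD. A residual SD of about 1,445 steps is needed for 80%.

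Add that the primary result will be read from its estimate and confidence interval, and that non-significance will not be taken as absence of a 1000-step effect.

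The cost is a wording change in two places and a less favourable stated figure. Enrolment and procedures do not change.

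### The stated 80% power for a 1,000-step difference does not follow from the stated inputs: it is about 30% if 2,500 is the SD of the analysed outcome, and 80% needs an unstated baseline correlation of about 0.82

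*Combined protocol and SAP*

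**What the plan says.** Section 5.4 (Accrual) plans 100 randomized participants, 50 per arm, with an SD of 2,500 steps, and says this "will ensure at least 80% power to detect a 1000 step difference". It assumes 10% dropout and a "conservative Bonferroni adjustment of the type I error rate with a 2-sided alpha of 0.017". Section 9 (Analysis plan) repeats the calculation, introducing it with "For these outcomes, we estimate a standard deviation of 2500 steps" straight after a sentence on subgroup analyses that ends "higher levels of social support on 1o and 2o outcomes".

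Section 3.1 gives one primary outcome, "change in mean daily step count from the baseline period to the end of the 12-week intervention period". Section 3.2 gives one secondary outcome, "mean daily step count during the 6-week follow up period after the end of the intervention". Section 3.3 lists functional and cognitive tests as exploratory. In Section 9, "the primary analysis will fit mixed effect regression models to evaluate changes in physical activity (steps per day and minutes of MVPA"), with adjustment for each participant's baseline and for repeated measures. MVPA is not in Section 3, and step count is the only tracker measure in Section 8.3.

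Neither power statement says what kind of SD 2,500 is, gives a correlation between baseline and outcome, or lists the tests that share the 0.017.

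**The concern.** A difference of 1,000 against an SD of 2,500 is a standardized difference of 0.4. Fifty per arm is few for an effect of that size at 80% power, and a level stricter than 0.05 makes it harder still. If the figure is wrong, a null result would be reported as coming from a trial with at least 80% power for 1,000 steps, when its real chance of detecting that difference may have been far lower. Readers would take the null as firmer evidence of no effect than it is.

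A smaller matter sits beside this. The level 0.017 looks like 0.05 split three ways, but Section 3 supplies only two primary and secondary outcomes. An MVPA result from the primary model would have no declared status.

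**Working it through.** **Inputs** (Sections 5.4 and 9): difference 1,000 steps; SD 2,500; 50 per arm; 10% dropout, so 50 × 0.9 = 45 evaluable per arm; 2-sided alpha 0.017. The method is a two-sample noncentral t with one value per participant, as an approximation to the planned mixed model.

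**Step 1. Try to reproduce the stated 80%, taking 2,500 as the SD of the analysed outcome.**
- Standard error = 2,500 × √(2/45) = 527.
- Noncentrality = 1,000/527 = 1.90; df = 2 × 45 − 2 = 88; critical t at 0.017 = 2.43.
- Power = 30.2%. The expected statistic is below the critical value, so power must be under one half.

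Variants, to see whether a different convention was used:

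| Evaluable per arm | 2-sided alpha | Power |
|---|---|---|
| 45 | 0.017 | 30.2% |
| 50 (no dropout) | 0.017 | 33.9% |
| 45 | 0.05 | 46.7% |
| 50 (no dropout) | 0.05 | 50.8% |

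One-sided testing does not rescue it: 50 per arm at one-sided 0.05 gives 63.9% (normal approximation). A figure near 80% (80.7%, normal approximation) appears with 100 per arm at 2-sided 0.05, which is not the stated design.

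**Step 2. Solve for what would give 80% at 0.017.**
- Detectable difference with 45 per arm and SD 2,500: about 1,730 steps (noncentral t). Normal approximation: (2.387 + 0.842) × 527 ≈ 1,700.
- SD needed for 1,000 steps with 45 per arm: about 1,445.
- Evaluable number needed for 1,000 steps with SD 2,500: 132 per arm.

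**Step 3. Allow for baseline adjustment.** If 2,500 is a raw SD, the residual SD is 2,500 × √(1 − ρ²), where ρ is the baseline-outcome correlation. The documents give no ρ, so these values are assumptions (45 per arm):

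| ρ | Residual SD | Power at 0.017 | Power at 0.05 |
|---|---|---|---|
| 0.5 | 2,165 | 40.9% | 58.2% |
| 0.7 | 1,785 | 59.0% | 74.8% |
| 0.8 | 1,500 | 76.6% | 87.9% |
| 0.816 | 1,445 | 80.0% | 90.1% |
| 0.9 | 1,090 | 97.1% | 99.0% |

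**Step 4. Change-score readings.** If 2,500 is already the SD of the change in Section 3.1, Step 1 applies and power is about 30%. If 2,500 is raw and a simple change is analysed, the SD of change is 2,500 × √(2(1 − ρ)). Setting that to 1,445 gives ρ = 1 − (1,445/2,500)²/2 = 0.83.

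**Step 5. Count the tests behind 0.017.** 0.05/3 = 0.0167, which rounds to 0.017; 0.05/2 = 0.025. Two arms give one contrast per outcome. One primary plus one secondary outcome makes two tests, so 0.017 implies a third that is not named. The divisor of three is an inference, since the documents state neither 0.05 nor 3.

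**The case against.** The strongest reply is that the planned model adjusts for baseline and uses repeated measures, so 2,500 may be a raw SD and the analysed SD smaller. That stands as a possibility, and it is why 30% cannot be asserted as the trial's true power. A reader might infer that the trial is simply underpowered at 30%. The documents do not support this, because they do not say which SD 2,500 is. Nor does the reply rescue the claim as written, since 80% then depends on a correlation of about 0.82 that appears nowhere.

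A second reply is that this is a pilot. The statement in Section 9 that the pilot is not adequately powered is attached to the exploratory subgroup analyses; the main comparison is described as having at least 80% power.

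On the level, a reader might infer inflated type I error, or that no result has a clear confirmatory status. Neither follows. Testing at 0.017 is valid and conservative, Section 3 tiers every outcome it lists, and Section 9 labels the subgroup, functional and cognitive analyses exploratory. Only MVPA lacks a tier. It is also tempting to say that MVPA must be the third test. It is a candidate, but the power sentence is in steps and follows a sentence on subgroups, so the third test cannot be identified from the text. Finally, nothing in the documents calls for replacing 0.017 with a hierarchical scheme at 0.05; that would relax the only written level and is a design preference.

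**Conclusion.** The power statement is unsupported as written. At the stated level it falls short of 80% by about 50 points if 2,500 is the SD of the analysed outcome, including a change-score SD. The shortfall is about 39, 21 and 3 points if 2,500 is a raw SD and the assumed correlation is 0.5, 0.7 or 0.8. The strict level does not by itself explain the gap, since 0.05 gives only 47% on the first reading. These figures rest on 45 evaluable per arm and one summary value per participant. The mixed model could differ somewhat, but the documents give no variance components with which to check it.

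The unnamed family of tests is a reporting gap. The only documented inconsistency there is that MVPA is in the primary analysis in Section 9 and has no tier in Section 3.

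**What to change.** In Sections 5.4 and 9:

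1. Say whether 2,500 is a raw, change-score or baseline-adjusted SD, and give any correlation assumed, with its source.
2. Restate the power for 1,000 steps, or the detectable difference, for 100 randomized at 2-sided 0.017. If 2,500 is the analysed SD, that is about 30% power, or about 1,730 steps at 80% power.

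As a minor correction, dated before outcome data are seen by arm:

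3. Keep the written 0.017 and name the tests it covers.
4. Make Sections 3 and 9 agree on MVPA, either by giving it a tier in Section 3 or by removing it from the primary-analysis sentence. If it stays, list it as a measure in Section 8.3.

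The work is one recalculation and some wording, with no change to enrolment, visits or data. The real cost is that the stated figure may be less favourable: if it falls to about 30%, the trial remains as small as it is, and a null result would have to be reported with that limitation.
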